Egg Desensitization and induction of tolerance in Children

Principal Investigator: [name] MD

McGill University Health Center

Sub-Investigators: [name] MD

McGill University Health Center

[name] MD

McGill University Health Center

1 Proposed Research Questions

1. What is the rate of desensitization in children allergic to egg?
2. What are the predictors associated with success or failure of desensitization in children?
3. What are the molecular mechanisms involved in desensitization?

2 Research Objectives and Significance

We are proposing to initiate a study assessing desensitization for egg

This study would enable us to better determine the potential benefit of desensitization in individuals with egg allergy.

More specifically, we will address the following research objectives:

Objectives

- A. To determine the rate of desensitization to egg..
- B. To characterize predictors of successful desensitization.
- C. To characterize molecular mechanisms involved in the process of desensitization.

3. Gaps and Unmet Needs in Existing Knowledge on food desensitization

3.i Why do we need trials on food desensitization.

Foods are reported to be primary inciting allergens for anaphylaxis and account for 33.2% to 56% of all anaphylaxis cases.⁽¹⁻⁴⁾ Further, food-induced anaphylaxis hospital admissions are reported to have increased, mainly in the first 2 decades of life.^(5;6) At present, the only treatment for food allergy is to avoid the allergy-causing food, while the only treatment for an allergic reaction is prompt administration of intramuscular epinephrine.^(7;8) Primary anaphylaxis prevention is based on allergen desensitization through immunotherapy and until recently was not available for food allergies. Although there are a few recent research protocols exploring desensitization for foods and although these have so far been largely successful,^(9;10) up to this point there are no known guidelines describing the optimal candidate for desensitization nor are there criteria for the safest and most effective dosing schedule. Further, many of these studies have a very small sample size and do not use a control group. Hence, the efficacy of these protocols is hard to interpret⁽¹¹⁻¹⁴⁾ and additional larger scale randomized control studies are required.

3.ii Why Egg.

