Desensitization will begin with combined challenge/rush desensitization. After placement of an intravenous catheter, 20 ml blood samples will be collected, skin prick test (SPT) to egg will be performed and 5 ml of saliva will be collected. These samples will be used to establish participants' baselines for the various biological markers being examined during the study. The modified challenge will begin with a first single dose of 0.1 mg of placebo, alternating with powdered egg white in the form of Meringue powder. After the initial dose, subjects will receive approximately doubling doses every 30 minutes until the highest tolerated single dose will be determined (see Appendix B for Challenge/Rush doses). For doses of 25 mg and greater, powdered meringue will be dispensed from individual preweighed containers.. After the initial dose, subjects will receive approximately doubling doses every 30 minutes until the highest tolerated single dose was determined. All doses will be mixed with an acceptable vehicle food chosen by the subject and his or her parent. Subjects treated for reactions will be observed for 2 hours, and if there is no evidence of an allergic reaction, they will be discharged home. Self-administered epinephrine will be provided to all patients' caregivers, along with instructions and indications for administration and education about the nature of possible reactions to OIT. To ensure there were no ill effects of the daily dosing, each subject will return to the CIM on the second day for an observed administration of the starting daily dose.

All challenges and escalation doses will take place in the Center of Innovative medicine (CIM) as is currently done for our milk and peanut desensitization study . The CIM services include equipment and medications required to monitor and treat potential reactions . The CIM nurse that will assist in the desensitization protocol is a nurse that has been trained to work in an intensive care unit. The patients will not be admitted, but will remain under observation for 7 h each day, with the possibility for increasing this period if required.

SPT with the allergens listed above will be performed on all patients before starting desensitization, and the tests will be repeated at 3, 6 and 12 months. Blood tests will be also performed to measure sIgE and sIgG, T cell phenotypes (including regulatory Tcells), salivary IgA and DNA methylation before desensitization, at 3 weeks and at 3, 6 and 12 months.

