The patients' parents will be instructed verbally and in writing about the recommendations to be followed after desensitization and how to treat possible allergic reactions. They will also given a direct telephone line for consultation. Patients will be instructed not to perform physical exercise ^(70;71) for 2 h after eating egg and not to take non-steroidal anti-inflammatory drugs for 3 h before or after ingestion. No special recommendations will be given for viral infections.⁽¹¹⁾ Participants will be given

symptom diaries and instructed to complete it daily to keep track of their allergic symptoms during the desensitization process.

Participants who are not able to achieve desensitization (desensitization defined as being able to tolerate the 300 mg maintenance dose) by 18 months following the initiation of the desensitization process will be considered treatment failures and discontinued from the study.

Maintenance/ Follow-up Phase

Once subjects reached the daily dose of 300 mg, they will be instructed to take this daily for the length of the study (12 months). The subjects will be also instructed to otherwise continue an egg-elimination diet for the duration of the study. Subjects and families will be asked to complete daily home diaries to document that daily doses were taken, as well as to report accidental ingestions, problems with dose administration, or related symptoms. Follow-up visits in addition to and in conjunction with the biweekly visits for dose escalation will be planned at 3, 6, 9, 12 months from the second egg challenge. Each visit will involve a medical history and physical examination. egg specific skin prick testing (SPT), a blood draw similar to that at the challenge to measure serum egg-specific IgE and IgG concentrations, T cell penotyping and DNA methylation. A 5 ml saliva sample will be collected to assess salivary IgA

Food challenges

One month after subjects reach the 300 mg dose, they will undergo a second food challenge to determine his or her allergenic reactivity to egg protein. Subjects will continue OIT dosing through the day before the challenge. The challenge will consist of 10 doses of powdered egg white given every 10 to 20 minutes in increasing amounts up to a total of 8 g of powdered egg white (6 g of egg protein).

After their year in the control arm, , oral desensitization will be offered to the control patients

Variables measured. The following variables will be measured in each patient:

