At the initial visit and at all follow-up visits, participants will be asked to produce 5 ml of saliva. Our work in previous desensitization studies has demonstrated that even children as young as 6 years can produce this volume of saliva. Egg-specific salivary IgA will be determined by ELISA

5. Statistical Considerations

Given that previous studies in adults have attributed at least 50% improvement in the ability to tolerate egg ⁽⁷⁵⁾ with an α of 0.05 and a power ($1 - \beta$) of 0.80, a sample of 17 cases and 17 controls will be recruited. Statistical analyses will be performed using paired t-tests. A P value of <0.05 will be considered significant.

Descriptive statistics of the variables including means, standard deviations and frequencies were computed for all study variables. The concentrations of egg -sIgE and sIgG , the weal size , Mast cell, salivary IgA, T cell and DNA methylation status at the different study time-points will be compared with their baseline values using the one-sample paired t-test and to the control using a 2 sample t-test .

Multiple regression models will be used to assess factors associated with response to desensitization (i.e. baseline demographic characteristics; gender; age; baseline basophile

activation; T cell status, baseline SPT and specific IgE, salivary IgA, and DNA methylation status,).

6. Ethical Considerations

In the consent form given at study enrolment, participants will be advised that they will be randomly assigned to either desensitization treatment or observation alone for one year, (appendix B). Participants will also be advised that their data will be shared only among the study members. Participants who will be at the control group will be told that they will be offered the desensitization protocol one year after study entry.

7. Participant Confidentiality and Record Retention

All participants will be assigned a unique study code that will be used on all study documents. The link between the participants' code and their name will be stored on a password protected computer in the MUHC's Centre for Innovative Medicine, which is a restricted access unit. All study documents will be kept in a locked filing cabinet in the Centre for Innovative Medicine. Only members of the study team, and authorized oversight bodies will be allowed access to the study documents.

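### At least 54 marker t-tests at 0.05, half of them within arm and with no key time: chance findings are likely, and natural change can pass for a treatment effect

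*Combined protocol and SAP*

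**What the plan says.** Section 5 sets one criterion for all analyses: "A P value of <0.05 will be considered significant". It then lists the markers, "The concentrations of egg -sIgE and sIgG , the weal size , Mast cell, salivary IgA, T cell and DNA methylation status", and states that at the different time points they "will be compared with their baseline values using the one-sample paired t-test and to the control using a 2 sample t-test". It names no leading marker or time, gives no testing order or multiplicity adjustment, and does not call these analyses exploratory.

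The times are in Section 4. Under the egg desensitization heading, the blood and saliva markers are taken "before desensitization, at 3 weeks and at 3, 6 and 12 months", while for skin prick testing "the tests will be repeated at 3, 6 and 12 months". The maintenance and follow-up text gives a different clock: visits "will be planned at 3, 6, 9, 12 months from the second egg challenge". The basophil test, which stands in for mast cell activation, is in neither list.

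Of the seven markers, six are listed as secondary variables in Section 4. Methylation is not on that list, but it is in the visit schedule and in Section 5. Weal size, sIgE and sIgG are filed there as indices of desensitization. The other four (basophils, T cells, salivary IgA, methylation) bear most directly on Objective C in Section 2: "To characterize molecular mechanisms involved in the process of desensitization".

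**The concern.** There are two separate problems.

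- **Number of tests.** A rule of P<0.05 on each of several dozen tests will usually produce some significant results by chance, and the plan does not say in advance which result counts.
- **Type of comparison.** A paired test within the treated arm measures change since baseline, not change caused by treatment. Section 3.ii itself gives reasons to expect change without treatment: egg allergy resolves in part with age, and avoidance is said to raise sensitization. A control arm exists to remove such change, and the paired test does not use it. Adjusting for multiplicity would not cure this.

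Mechanism is one of three objectives, so a reported marker change is likely to be read as a finding about how desensitization works.

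**Working it through.** **The plan's own figures.** The documents state no number of tests and no family-wise error rate, so there is nothing to reproduce. The 17 + 17 sample size is argued from tolerance of egg, not from any marker.

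**Count.** Six markers at 4 post-baseline times plus weal size at 3 times gives 6 × 4 + 3 = 27 marker-times. Two tests each gives 27 × 2 = 54. This assumes that basophils follow the other blood markers. The alternative schedule (3, 6, 9, 12 months for all) gives 7 × 4 × 2 = 56. Both counts are minimums: Section 4 describes T cell phenotype, Tregs, cytokine release and responses to several antigens, and basophil CD63 with more than one antigen. The four markers outside the indices of desensitization give 4 × 4 × 2 = 32.

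**Expected false positives (no effect, no time trend).** 54 × 0.05 = 2.7; for the four markers, 32 × 0.05 = 1.6. These hold whatever the correlation.

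**Chance of at least one.** If all tests were independent: 1 − 0.95^54 = 93.7%, and 1 − 0.95^32 = 80.6%. The tests are not independent and the documents give no correlations, so I simulated a range: 17 per arm, normal data, equal correlation over time, paired test in the treated arm, two-sample test on the values at each time, 4,000 null trials per case.

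| Correlation between markers | Correlation over time | 54 tests | 32 tests |
|---|---|---|---|
| 0 | 0.5 | 89% | 74% |
| 0 | 0.8 | 88% | 69% |
| 0.3 | 0.5 | 87% | 72% |
| 0.3 | 0.8 | 83% | 68% |
| 0.5 | 0.5 | 82% | 67% |
| 0.5 | 0.9 | 75% | 59% |

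Using changes from baseline in the two-sample test moves this little: about 77-87% on the 56-test count.

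**Natural change.** Assume both arms drift equally and linearly to 0.3 SD at 12 months, with no treatment effect. The SD of a child's change is √(2(1 − r)) in units of the marker SD, so at 12 months the paired test sees 0.3/1.00 = 0.30 (r = 0.5) or 0.3/0.632 = 0.47 (r = 0.8). Over the 54 tests the mean number significant rises from 2.7 to 4.1 (r = 0.5) or 6.5 (r = 0.8), and the chance of at least one to 94% or more. The excess comes from the paired tests; equal drift cancels in the two-sample tests.

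**Gain from baseline adjustment.** At a single time, adjustment multiplies the variance of the arm difference by 1 − r²: 0.75 at r = 0.5 and 0.36 at r = 0.8, a cut of 25% or 64%. With 17 per arm, an unadjusted two-sample t-test has 80% power for a difference of 0.99 SD. Adjusted, this becomes about 0.99 × √0.75 = 0.86 SD or 0.99 × √0.36 = 0.59 SD.

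**Which adjusted comparison.** Averaging all four visits looks better still, with variance factor (1 + 3r)/4 − r² = 0.375 (r = 0.5) or 0.21 (r = 0.8). But if the effect grows linearly to 12 months (an assumption), the average effect is only (0.058 + 0.25 + 0.50 + 1)/4 = 0.45 of the 12-month effect. For a 12-month effect of 1 SD and 17 per arm:

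- unadjusted two-sample t-test at 12 months: 81% power;
- adjusted four-visit average: 55% (r = 0.5) to 80% (r = 0.8);
- adjusted comparison at 12 months: 90% (r = 0.5) or more.

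So under a gradual effect the average can do worse than the planned test, while the adjusted 12-month comparison does better.

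**The case against.** The strongest reply is that these are secondary marker analyses in a 34-child study, that such p-values are commonly left unadjusted, and that readers will discount them. Part of this stands. The primary variable is tolerance of egg, and its error rate is not touched. But the plan does not label the marker tests as exploratory, and the label would not make a within-arm change into a treatment effect.

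Some stronger readings are tempting but not supported:

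- **That a false mechanistic finding is 85-90% likely under Objective C.** The documents file three of the seven markers elsewhere and give no correlations. For the other four, the range is about 60-80%, and it applies only if there is no effect on any of them and no time trend.
- **That the two-sample tests ignore baseline.** Section 5 does not say whether they use values or changes. The fair statement is that no use of baseline is specified.
- **That a false result could not be told from a real one.** Agreement across times, and between the two kinds of test, would still be visible. The plan just does not say how it would be weighed.

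**Conclusion.** The point holds as a low-cost improvement to the secondary analyses. At least 54 tests at 0.05 give about 2.7 expected false positives when there is no effect and no time trend. The chance of at least one is roughly 75-95%; the lower end rests on strong assumed correlations and the upper end on independence. No case tried came near 5%. The paired tests are the more serious half, because natural change over the year can appear as an effect of treatment; the 4-6.5 figure rests on an assumed drift of 0.3 SD. The variance gain of 25-64% rests on an assumed baseline correlation of 0.5 to 0.8.

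**What to change.** In Section 5, base inference for each marker on the between-arm difference at one prespecified time, adjusted for the child's baseline value. Twelve months from the start of the trial is the natural choice, because it lies within the controlled year. State that clock explicitly: controls are offered desensitization after a year and, on the plan as written, have no comparable second challenge to count from. Use ANCOVA, or a longitudinal model with an arm-by-time term and its 12-month contrast, with sIgE and sIgG on the log scale. Name one readout each for T cells, basophils and methylation; without that the count is not seven.

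Report within-arm changes and the other times as descriptive estimates with confidence intervals. Benjamini-Hochberg q-values beside the p-values are optional. Seven tests leave 7 × 0.05 = 0.35 expected false positives and, if independent, a 1 − 0.95^7 = 30% chance of at least one before any adjustment.

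The cost is a change of SAP wording and slightly more analysis work, with no added visits, samples or children. Fewer markers will be nominally significant. An early effect that fades by 12 months would show only in the descriptive estimates, unless another time is prespecified for that marker.

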Egg allergy is the most common IgE mediated food allergy in children. Approximately 30% of children suffering from moderate to severe atopic dermatitis present an associated food allergy and egg is reported to be the major food allergen triggering IgE mediated allergic reactions in those with atopic dermatitis.⁽²⁶⁾ The major allergens in egg are known as Gal d 1-5 and include Ovomuroid which is the dominant egg allergen,(Gal d 1) and is a protease inhibitor, Ovalbumin (Gal d 2) & Ovotransferrin (Gal d3) and lysozyme (Gal d4).⁽²⁷⁾ Egg allergens are altered by heat and gastric enzymes and 55%-73% of those with egg allergy will be able to ingest cooked egg.^(28;29) However, ovomucoid, the main egg allergen, is not affected by heating.⁽³⁰⁾ Different egg whites (e.g. goose , duck and turkey) were all found to contain proteins cross-reacting with most of the allergens in hen's egg white.⁽³¹⁾ Presence of egg allergy has also major implications regarding safe administration of vaccines. Several vaccines are manufactures on egg containing media including yellow fever and Q fever and may induce an allergic reaction in those that are egg allergic.⁽³²⁻³⁵⁾ Hence, use of rapid and effective desensitization to egg may be extremely beneficial prior to travel to yellow fever endemic areas. In addition, although

it was reported that the median age for tolerance to egg is 6 years \pm 6 months,⁽³⁶⁾ recent studies suggest a lower resolution rate of 68% by age 16 years.⁽¹⁷⁾

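### Section 5 gives an uncontrolled change-from-baseline test of each marker the same standing as the comparison with the randomized control, though only the latter tests an effect of desensitization

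*Combined protocol and SAP*

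**What the plan says.** Section 2 lists as objective C: "To characterize molecular mechanisms involved in the process of desensitization". The analysis serving it is in section 5, where the marker values at each study time point "will be compared with their baseline values using the one-sample paired t-test and to the control using a 2 sample t-test". Two other sentences in section 5 bear on how these tests are read. One is general: "Statistical analyses will be performed using paired t-tests". The other sets a single threshold: "A P value of <0.05 will be considered significant". Section 5 does not say which of the two marker tests decides objective C, whether both must be positive, or how to read a marker that is significant on one only. It also leaves open whether the two-sample test uses follow-up values or changes from baseline.

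The control arm is concurrent, randomized 1:1, untreated and followed up (sections 3.ii and 4).

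**The concern.** The two tests have different null hypotheses. The paired test's null is zero mean change over time within one arm. Anything that moves the marker will reject it, treated or not. The two-sample test against the randomized control has the null that objective C needs, namely no effect of desensitization, because a shift common to both arms cancels.

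The plan gives some reason to expect change without treatment. Section 3.ii notes that "recent studies suggest a lower resolution rate of 68% by age 16 years", and the children enrolled are 6 to 18 years old. That is a statement about clinical resolution, not about any marker, but it means a stable untreated course cannot be taken for granted. Section 3.i itself finds earlier desensitization studies hard to interpret because they lacked controls. A within-arm test that carries the label of significance brings the same weakness into the marker results.

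At stake is whether a marker that moved equally in both arms is reported as part of the mechanism. The bias acts on each single test. It is not a multiplicity problem, and a stricter P value does not cure it.

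**Working it through.** **The plan's own figure.** Section 5 states that "a sample of 17 cases and 17 controls will be recruited", for α 0.05, power 0.80 and a 50% improvement in tolerated egg. It gives no SD and no response rates, so 17 cannot be derived from what is stated. Read as a two-sided comparison of two means, 17 per arm has 80% power for a standardized difference of about 0.96 (normal approximation: (1.960 + 0.842) × √(2/17) = 0.961) or 0.99 (exact t). The documents state no error rate for the marker tests beyond the 5% threshold.

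**Inputs for the check.**
- n = 17 per arm, threshold 0.05 (section 5). Sidedness is not stated; two-sided is assumed.
- The paired test is applied to the treated arm.
- No treatment effect, and the same mean drift in both arms of d SDs of the individual change. The documents give neither a marker drift nor an SD of change, so d is an assumption and is shown over a range.

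**Paired test against baseline.** The statistic is noncentral t with 16 degrees of freedom and noncentrality √17 × d = 4.123 × d. It rejects when |t| > 2.120.

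| Drift d (SD of change) | Noncentrality | P(reject) |
|---|---|---|
| 0 | 0 | 5.0% |
| 0.1 | 0.41 | 6.7% |
| 0.2 | 0.82 | 12.1% |
| 0.3 | 1.24 | 21.4% |
| 0.5 | 2.06 | 49.1% |
| 0.75 | 3.09 | 82.7% |

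Solving the other way, the rate reaches 10% (twice nominal) at d of about 0.17 and 15% (three times nominal) at about 0.24.

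**Two-sample test against control.** The common drift cancels in the difference between arms. In 40,000 simulated trials per setting, with drifts of 0 to 0.75 and baseline-to-follow-up correlations of 0.5 and 0.8, it rejected 4.9% to 5.2% of the time, whether run on follow-up values or on change.

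**What the missing rule does.** In the same simulations, with the two-sample test on follow-up values:
- If either test may establish a marker, the false-positive rate is 9.6% with no drift, about 20% at d = 0.25 and about 52% at d = 0.5.
- If both must be positive, it is 0.4% to 4.0% over the whole range.
- At d = 0.5 and correlation 0.5, the paired test is positive in 49.6% of trials and both tests in 2.6%. So (49.6 − 2.6)/49.6 = 95% of the significant paired results have a non-significant comparison with control.

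**Matched time points.** Section 4, under the desensitization procedure, times marker blood samples before desensitization, at 3 weeks, and at 3, 6 and 12 months. The maintenance and follow-up subsection times visits with the same skin, blood and saliva measures at 3, 6, 9 and 12 months from the second egg challenge. That challenge comes one month after a child reaches 300 mg, so the second clock never starts for a control child, nor for a treated child who does not reach that dose. Controls are offered desensitization after their year. Matched control values are therefore not assured on the second clock.

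**The case against.** The strongest reply is that the quoted sentence already plans the right test. A reader might infer that section 5 puts a test of no change over time in place of a test of no treatment effect. The documents do not support that: the two-sample comparison is in the same sentence, has the right null, and holds 5% under common drift. The defect is equal standing, not omission.

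Second, the misuse is not written down. No rule says that a marker significant only against its baseline counts as a mechanism, and a paired test that rejects when a marker has truly moved is correct for its own null. The rates above become errors only when such a result is attributed to desensitization. That is fair. But the plan labels the paired result significant, gives no rule for disagreement, and names paired t-tests as its general method.

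Third, a reader might infer that the error rate is several times 5%. The documents do not support that as an unconditional statement. It needs a drift of about 0.24 SD of change or more, and at 0.1 SD the rate is only 6.7%. The 68% in section 3.ii is cumulative clinical resolution, not a 12-month shift in a marker, and the argument from maturation is weaker at 3 weeks and 3 months. Nothing in the documents points to assay or reagent drift, and the planned gliadin, tetanus toxoid and healthy-control comparisons give partial protection for the basophil and T cell assays. All of this stands and limits the claim about size.

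Finally, these are secondary variables, and dropping within-arm P values is partly a matter of reporting style. That also stands, though the markers are the whole evidence for objective C.

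**Conclusion.** The point holds in limited form. For every marker, section 5 gives an uncontrolled within-arm test the same 5% standing as the comparison with the randomized untreated arm, and only the latter speaks to an effect of desensitization. With 17 per arm, no treatment effect and equal drift in both arms, the paired test rejects 6.7% to 49% of the time for drifts of 0.1 to 0.5 SD of change; the between-arm test stays near 5%. The size rests wholly on the assumed drift, on two-sided testing and on approximately normal changes. The direction does not depend on the amount: any non-zero common drift pushes the paired test above 5%. The point concerns the marker analyses only, not the primary outcome. It is a cheap improvement that should be made, since the better test is already planned.

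**What to change.** 1. State in section 5 that a marker change is attributed to desensitization only on the between-arm comparison at the same time point, using change from baseline or, equally acceptable, the follow-up value adjusted for baseline (ANCOVA).
2. Report the within-arm change for both arms side by side as a mean with its 95% confidence interval, as description and without a significance label.
3. Reconcile the two sampling schedules in section 4 so that treated and control marker samples are taken on one clock counted from study start, and state explicitly that controls are sampled at those points.

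The first two changes are a couple of sentences and need no measurements beyond those the planned two-sample test already requires. The third may need a revised visit table, and it may add control samples if none were intended at some points. The statistical cost is fewer nominally significant markers: with 17 per arm the between-arm test has 80% power only for a difference of 0.99 SD, so moderate marker effects will often be missed. The confidence intervals will show that uncertainty openly.

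### The between-arm marker comparisons are specified as 2-sample t-tests with no stated use of each child's own baseline, which can cost precision and leaves each result exposed to chance baseline imbalance

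*Combined protocol and SAP*

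**What the plan says.** Section 5 lists sIgE, sIgG, weal size, mast cell, salivary IgA, T cell and DNA methylation results. It plans two comparisons for each and names the tests as follows: "using the one-sample paired t-test and to the control using a 2 sample t-test". The first of these is the within-child comparison, in which follow-up results are set against the child's own starting level; the second sets the treated arm against the control arm. The threshold is stated once: "A P value of <0.05 will be considered significant".

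The only regression in section 5 has a different purpose: "Multiple regression models will be used to assess factors associated with response to desensitization". It looks for predictors of response and does not estimate the effect of arm on a marker.

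Baseline values are planned. Section 4, under Desensitization to egg, takes blood, a skin prick test and saliva to set participants' "baselines for the various biological markers being examined during the study". The schedule there includes "salivary IgA and DNA methylation before desensitization, at 3 weeks and at 3, 6 and 12 months". The list under Variables measured opens with "The following variables will be measured in each patient", without restriction to one arm.

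Randomisation uses age and sex according to section 3.ii, and sex alone according to section 4. Neither balances the arms on any marker.

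**The concern.** Objective C, on mechanisms, rests on these markers. Two tests are planned for each, and each lacks what the other has. The paired test uses the child's own baseline but has no control group, so it cannot separate treatment from ageing or natural resolution; section 3.ii itself cites 68% resolution by age 16. The 2-sample test has the control group but, as written, no baseline.

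The randomised comparison would then leave out what is often a strong predictor of a child's follow-up value. With 17 per arm two things are at stake: power to detect a real effect on a marker, and the credibility of a between-arm difference when the arms happened to start apart on that marker.

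**Working it through.** **The plan's own figure.** The 17 per arm (80% power, alpha 0.05) is tied to a 50% improvement in tolerated egg, not to a marker, and no SD is given. It cannot be derived from the stated inputs. It does match a two-sided 2-sample t-test for a 1.0 SD difference, which needs 16.7 per arm and has 80.7% power at 17. The plan gives no power for the markers.

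**Inputs.** From the documents: n = 17 per arm, N = 34, alpha 0.05. Assumed: a two-sided test, a true marker difference of 0.7 SD, and r from 0 to 0.9. The documents give neither r nor a marker effect size.

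**Chance imbalance.** The SE of the baseline difference between arms is sqrt(2/17) = 0.343 SD. A difference above 0.5 SD lies beyond 0.5/0.343 = 1.46 SE, so its two-sided probability is 0.145, about 14% of trials for each marker. Such an imbalance shifts the expected follow-up difference by r × 0.5 SD: 0.15, 0.25, 0.35 and 0.40 SD at r = 0.3, 0.5, 0.7 and 0.8.

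**Error rates.** I simulated trials with no treatment effect, 40,000 for each r. Over all trials, both the t-test and ANCOVA reject in about 5%. Among trials with a baseline imbalance above 0.5 SD, the t-test rejects in about 8%, 12%, 19% and 25% at r = 0.3, 0.5, 0.7 and 0.8, and ANCOVA in about 5%. Monte Carlo error on the conditional t-test figures is about half a percentage point.

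**Precision.** Adjustment lowers residual variance by r². Estimating the slope costs a factor 1 + 1/(N − 4) = 1 + 1/30 = 1.033. The variance relative to the t-test is therefore (1 − r²) × 1.033, with 31 degrees of freedom instead of 32. The equivalent sample size for the t-test is 17 divided by that ratio. At r = 0.7: 1 − 0.49 = 0.51; 0.51 × 1.033 = 0.527; 17/0.527 = 32.3. Power comes from the noncentral t distribution; the unadjusted t-test has 50.8%.

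| Assumed r | Fall in residual variance (r²) | Variance ratio after cost | Equivalent n per arm | ANCOVA power |
|---|---|---|---|---|
| 0 | 0% | 1.033 | 16.5 | 49% |
| 0.2 | 4% | 0.992 | 17.1 | 51% |
| 0.3 | 9% | 0.940 | 18.1 | 53% |
| 0.5 | 25% | 0.775 | 21.9 | 61% |
| 0.7 | 49% | 0.527 | 32.3 | 78% |
| 0.9 | 81% | 0.196 | 86.6 | 99% |

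**Change score.** Its variance relative to the follow-up-only t-test is 2(1 − r). At r = 0.3 this is 1.4, and power is 39%. At r = 0.5 it is 1.0, with no gain. At r = 0.7 it is 0.6, and power is 72%, against 78% for ANCOVA.

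**The case against.** The planned test is sound as a test. A reader might infer from the 14% figure that the marker results are biased or that the t-test is invalid. The documents do not support that: allocation is randomised 1:1, and the t-test's standard error already allows for chance imbalance, so its error rate is 5% over all randomisations. What remains is lost precision, and a higher error rate given that a large imbalance has occurred.

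The text also does not say that raw follow-up values go into the 2-sample test; changes from baseline may be meant. This stands as a point about wording: the claim is that no adjustment is specified, not that baseline is certainly ignored. Section 5 would still need correcting, because a change score is less precise than the follow-up value alone when r is below 0.5.

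The correlation may be low for some markers. They are measured from 3 weeks to 12 months after baseline, under a treatment meant to change them, and one r need not fit all. This stands too: below about 0.3 the gain is nil to small.

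Finally, baseline sampling in control children is not spelled out. The skin test sentence reads "SPT with the allergens listed above will be performed on all patients before starting desensitization", and controls are not desensitised during the trial year. The reference to each patient, and saliva at the initial visit, imply a control baseline but do not schedule one.

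**Conclusion.** The point holds as a recommendation on efficiency for secondary, mechanistic variables; it does not touch the primary outcome. No baseline adjustment is specified for the arm contrast on any marker. At a 0.7 SD difference, adjusting moves power from 51% to somewhere between 49% and 99%. The gain becomes material from r of about 0.5 (61%, worth about 22 per arm) and is large at 0.7 (78%, worth about 32 per arm). These figures assume a two-sided test, a continuous marker on a scale where a linear model fits, complete data on all 34 children, and a value of r that only the data can supply.

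A reader might also infer that a mechanism will be claimed from the within-arm test when the between-arm test fails. The documents do not say so: section 5 plans both comparisons and ranks neither. It is a risk that the plan leaves open.

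**What to change.** In section 5, replace the 2-sample t-test for each continuous marker with ANCOVA of the follow-up value on arm, that marker's own baseline and the randomisation factor(s). Name the scale for each marker, for example log for sIgE and sIgG. Report the adjusted arm difference with its 95% CI as the evidence for objective C, and describe within-arm changes without using them as evidence of a treatment effect. A basophil result analysed as positive or negative falls outside this model and needs its own method.

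Two statements elsewhere must be settled first. Sections 3.ii and 4 should agree on the randomisation factors, so that the model can include them. Section 4 should state that control children give the baseline sample, and when their follow-up samples fall.

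The cost is a few sentences, one degree of freedom for the baseline and one or more for the randomisation factor(s), and about 1 to 2 points of power if r is near zero. No new data are needed if the control baseline sample is already intended.
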